## 4.0 Test Schedule

### 4.1 Test schedulea

Tests and Procedures	≤28 days prior to registration	≤14 days prior to registration	Cycle 1, Day 1	Cycle 1, Day 15	Cycle 2 (to 4 † ), Day 1	Cycle 2 (or 4 † ): ≤14 days prior to ASCT	Cycle 3 (or 5 † ): Day 100 visit of ASCT (occurs 90-110 days after ASCT)	Cycle 4 (or 6 † ) and beyond (end of each cycle)	End of Treatment
Complete medical and disease history		X			X	X	X	X	
Physical examination b		X			X	X	X	X	
Electrocardiogram (ECG)		X							
Performance status (ECOG scale)(Appendix 1)		X			X	X	X	X	
CBC with differential		X	X c	X	X	X	X	X	X
Type and Screen			X						
Prothrombin time (PT) and INR		X	X c	X	X	X	X		
Blood chemistries: sodium, chloride, potassium, magnesium, phosphate, uric acid, BUN, glucose, ALT/AST (SGPT/SGOT), alkaline phosphatase, total protein, Direct bilirubin, total bilirubin, albumin, serum creatinine, and estimated creatinine clearance (Appendix II), calcium and lactate dehydrogenase (LDH)		X	X c	X	X	X	X	X	X

Tests and Procedures	≤28 days prior to registration	≤14 days prior to registration	Cycle 1, Day 1	Cycle 1, Day 15	Cycle 2 (to 4 † ), Day 1	Cycle 2 (or 4 † ): ≤14 days prior to ASCT	Cycle 3 (or 5 † ): Day 100 visit of ASCT (occurs 90-110 days after ASCT)	Cycle 4 (or 6 † ) and beyond (end of each cycle)	End of Treatment
Bone marrow aspirate/biopsy with standard testing (including but not limited to myeloma FISH and flow cytometry) d	X					X d	X	X	
Bone marrow MRD Assessment by MPF d	X					X	X	X	
Peripheral blood MRD testing e	X					X	X	X	
Electrophoresis of serum and urine (SPEP/UPEP)		X			X l	X l	X l	X l	X*
*Serum immunoglobulins d		X			X	X	X	X	X*
*Immunofixation serum and urine (IF)		X			X	X	X	X	X*
*Immunoglobulin free light chain (FLC)		X			X	X	X	X	X*
*Serum β2-microglobulin		X							
Skeletal bone survey		X							
PET scan g	X							X	
Adverse Event monitoring f		X			X	X	X	X	X
Pregnancy test e		X						X	
Registered in the REVLIMID REMS™ program h							X		
Pill Diary i								X	

**Cycle 1 (to 3, as the case may be for that patient)** = 28 days (4 weeks)

**Cycle 2 (or 4, as the case may be for that patient)** = Up to 84 days (4 weeks treatment + window period up to 8 weeks between Consolidation 1 and ASCT)

**Cycle 3 (or 5, as the case may be for that patient)** = Up to 124 days (Day 100 visit of ASCT occurs 90-110 days after ASCT + window period up to 14 days between Day 100 visit and start of Maintenance)

**Cycles 4-15 (or 6-17, as the case may be for that patient)** = 28 days (4 weeks)

**Cycles 16 and beyond (or cycle 18 and beyond, as the case may be for that patient)** = 90 days (3 months)

†In case patient given cycle 3 and 4 optional treatment in consolidation 1, the subsequent cycle numbers and Day 100 ASCT visit will be adjusted accordingly.

All tests and procedures are clinically indicated, unless noted with an R to indicate funding by research

- a) All scheduled visits will have a window of  $\pm 3$  days, Cycle 1, Day 1, unless otherwise stated, all procedures to be completed within 3 days prior to commencing subsequent treatment cycle. ( $\pm 3$  days does not apply to daratumumab treatment in cycles 1-4; consolidation 1)
- b) To include blood pressure, pulse rate, temperature, weight. Height to be documented  $\leq 14$  days prior to registration
- c) Labs are not required to be repeated if done  $\leq 14$  days prior to registration.
- d) Standard of care procedure: Prior to Cycle 1, pre-ASCT, at Day 100, prior to Cycle 16 or if considered clinically indicated at any other time during the study. Bone marrow biopsy during cycle 2 can be done any time between days 28 and 84.
- e) To coincide with standard of care blood sample collection at: Prior to Cycle 1, pre-ASCT, at Day 100, prior to cycles 8, 12, 16, 18, and 20. NOTE: To coincide with the day of MRD testing by bone marrow biopsy, if occurring at that time point.
- f) Serum immunoglobulins to include IgG, IgA and IgM for all patients and IgD or IgE where clinically indicated. NOTE: bone marrow testing prior to registration must be after the last anti-myeloma treatment but  $\leq 28$  days of registration.
- g) A PET scan should be done within 28 days prior to registration, prior to Cycle 16 treatment and whenever else considered clinically necessary. PET scan done when CR considered to assess imaging response.
- h) During treatment period, at end of treatment visit. The patient should be contacted by a nurse 30 days after the last dose of study treatment (or at the time of initiation of subsequent treatment if started before 30 days) to check if the patient has experienced any late adverse events. Grade 3 or higher adverse events at least possibly related to study treatment and deaths due to any cause should be reported as a late adverse event on the Survival and Disease Status Follow-Up/Event Monitoring form if they were not already reported on the Adverse Event form for the last cycle and they occurred prior to any subsequent treatment and 30 days post-end of treatment
- i) For females of childbearing potential, a negative pregnancy test (urine or serum) must be documented within 14 days of starting treatment on the study and for patients starting Cycle 4 (daratumumab+lenalidomide) in accordance with the REVLIMID REMSTM program. A female of childbearing potential (FCBP) is a sexually mature female who: 1) has not undergone a hysterectomy or bilateral oophorectomy; or 2) has not been naturally postmenopausal for at least 24 consecutive months (i.e., has had menses at any time in the preceding 24 consecutive months).
- j) Patients starting Cycle 4 treatment (daratumumab+lenalidomide) prior to starting treatment with REVLIMID
- k) To be collected at the end of every cycle of maintenance therapy while the patient is receiving lenalidomide
- l) UPEP testing required at baseline only. Subsequent testing will be as needed per physician discretion.

\*Repeat Electrophoresis of serum and urine, Serum immunoglobulins, Immunofixation serum and urine, and Immunoglobulin free light chain only if the assessments were not completed 14 days prior to End of Treatment visit.

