When the study has been permanently closed to patient enrollment, submission of annual IRB approvals to the Registration Office is no longer necessary.

- 6.14 Treatment on this protocol must commence at Mayo Clinic under the supervision of a medical oncologist/hematologist.
- 6.15 Treatment cannot begin prior to registration and must begin  $\leq$  28 days after registration.
- 6.16 Pretreatment tests/procedures (see Section 4.0) must be completed within the guidelines specified on the test schedule.
- 6.17 All required baseline symptoms (see Section 10.6) must be documented and graded.
- 6.18 Study drug is available on site.

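### Footnote c of the test schedule makes the Cycle 1 Day 1 CBC, PT/INR and chemistry entries apply to no properly registered patient, so labs may be up to 42 days old at the first daratumumab dose

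*Combined protocol and SAP*

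**What the plan says.** Three laboratory rows in the section 4.1 schedule, "CBC with differential", "Prothrombin time (PT) and INR" and the row beginning "Blood chemistries: sodium, chloride, potassium", are marked both in the column for the 14 days before registration and at Cycle 1 Day 1. Their Day 1 marks carry footnote c: "Labs are not required to be repeated if done" within 14 days before registration. The row "Type and Screen" is also marked at Cycle 1 Day 1, without that footnote.

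Section 3.15 sets the same 14-day pre-registration window for the eligibility values: ANC, platelets, creatinine clearance, bilirubin, AST/ALT and PT/INR. Section 6.16 makes the schedule's pretreatment windows mandatory. Section 6.15 sets the time to first dose: "Treatment cannot begin prior to registration and must begin" no later than 28 days after registration.

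Two other footnotes use a different anchor. Footnote i says a negative pregnancy test "must be documented within 14 days of starting treatment on the study". Footnote a asks for "all procedures to be completed within 3 days prior to commencing subsequent treatment cycle", except where the schedule says something else.

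**The concern.** A Day 1 requirement with a conditional waiver makes sense only if some patients fail the condition. Here the condition is the same as the entry requirement, so nobody who is properly registered can fail it. The schedule appears to provide a pre-dose check of counts, coagulation and chemistry, but as written that check never has to be done.

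What is at stake is safety information at the first doses. Section 3.15 admits patients with an ANC of 1,000, and with platelets of 50,000, or 30,000 if marrow plasmacytosis is at least 50%. Section 15.15 lists neutropenia, thrombocytopenia and anemia as very common with daratumumab. The hold rules in section 8.3 let dosing resume on recovery to grade 2 or to baseline for hematologic events, so an old baseline is a weak reference. It also makes a cytopenia found at Day 15 harder to classify as new or pre-existing.

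**Working it through.** The plan states no figure for lab age at first dose, so there is nothing to reproduce. The check is one step of logic and some interval arithmetic.

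**Does the waiver ever fail?**
- Condition for the waiver (footnote c): labs done within 14 days before registration.
- Condition for registration (schedule column, sections 3.15 and 6.16): the same labs done within 14 days before registration.
- The two conditions coincide, so every properly registered patient qualifies for the waiver.
- Footnote a does not restore the draw. It concerns subsequent cycles and gives way to other statements in the schedule, and footnote c is such a statement for these three rows.

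**Inputs**
- Labs to registration: at most 14 days (section 4.1, section 3.15).
- Registration to first dose: at most 28 days (section 6.15).
- Daratumumab in Cycle 1 on Days 1, 8, 15 and 22 (section 7.11).
- Next required CBC: Cycle 1 Day 15 (section 4.1).

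**Formulas**
- Maximum age at first dose = (labs to registration) + (registration to first dose).
- Maximum age at the Day 8 dose = age at first dose + 7.
- Maximum gap to the Day 15 CBC = age at first dose + 14.

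| Quantity (maximum, days) | As written | Footnote c tied to Cycle 1 Day 1 |
|---|---|---|
| Lab age at first dose | 14 + 28 = 42 | 14 |
| Age of last required CBC at the Day 8 dose | 42 + 7 = 49 | 14 + 7 = 21 |
| Gap between required CBCs, up to Day 15 | 42 + 14 = 56 | 14 + 14 = 28 |

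The re-anchored version is shorter by 28 days at each point. These figures use nominal visit days. The ±3-day visit window and the ±1-day daratumumab window in section 7.0 are ignored; they would shift the last two rows by a few days.

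**The case against.** The strongest reply is that a test calendar sets a minimum and is not the only control on dosing. Section 7.11 refers daratumumab administration to prescriber information and institutional guidelines, section 6.14 requires treatment to begin under a medical oncologist or hematologist, and section 15.18 tells nursing staff to monitor the CBC. Fresher labs may well be drawn in practice. That stands as a reason to keep the point minor. It does not remove the point, because none of these provisions states a limit on lab age before the first dose.

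A second reply is that anchoring to registration is the protocol's usual convention. History, physical examination, ECG and performance status are also done within 14 days before registration and not repeated at Cycle 1 Day 1. This is true, but those rows do not list a Day 1 assessment and then cancel it.

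Third, the comparisons with footnotes i and a are imperfect. The pregnancy test also appears in the pre-registration column and in section 3.15, so the protocol uses both anchors for it. Footnote a's 3-day rule serves patients already exposed to the drug. Both comparisons therefore show only that the protocol uses treatment-based anchors elsewhere. The finding does not depend on them.

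Finally, no Day 1 laboratory threshold exists that an old result would cause to be missed, and no specific dosing decision has been shown to change. That also stands, and it limits the weight of the point.

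**Conclusion.** The concern holds, as a minor safety and schedule point. On the current text the three Cycle 1 Day 1 laboratory entries bind no properly registered patient, and the last required labs may be as much as 42 days old at the first daratumumab dose.

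The 42 days is reached only if labs are drawn a full 14 days before registration and treatment starts on the 28th day after it. The documents do not give the actual time from registration to first dose, so the typical age cannot be stated. The conclusion concerns what the protocol requires; a site may draw the labs regardless. The primary endpoint and the design's operating characteristics are not affected.

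**What to change.** Change the anchor in footnote c so that it reads: "Labs are not required to be repeated if done" ≤14 days prior to Cycle 1 Day 1. The maximum lab age at first dose falls from 42 to 14 days, and the Day 1 entries then apply to the patients who need them.

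The cost is one amended footnote and one repeat routine draw for each patient whose labs are more than 14 days old at first dose. It can be taken with the Type and Screen already required at that visit. The ceiling is 50 draws, one for each of the 50 planned patients in section 16.12. The true number will be lower to the extent that patients cancel before treatment or start promptly.

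The change does not add a count before Day 8, so that dose may still be given before a newer required CBC, though the last one would then be at most 21 days old rather than 49.

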## 10.1 Adverse Event Characteristics

**CTCAE term (AE description) and grade:** The descriptions and grading scales found in the revised NCI Common Terminology Criteria for Adverse Events (CTCAE) version 4.0 will be utilized for AE reporting. All appropriate treatment areas should have access to a copy of the CTCAE version 4.0. A copy of the CTCAE version 4.0 can be downloaded from the CTEP web site:

([http://ctep.cancer.gov/protocolDevelopment/electronic\\_applications/ctc.htm](http://ctep.cancer.gov/protocolDevelopment/electronic_applications/ctc.htm))

- a. Identify the grade and severity of the event using the CTCAE version 4.0.
- b. Determine whether the event is expected or unexpected (see Section 10.2).
- c. Determine if the adverse event is related to the study intervention (agent, treatment or procedure) (see Section 10.3).
- d. Determine whether the event must be reported as an expedited report. If yes, determine the timeframe/mechanism (see Section 10.4).
- e. Determine if other reporting is required (see Section 10.5).
- f. Note: All AEs reported via expedited mechanisms must also be reported via the routine data reporting mechanisms defined by the protocol (see Sections 10.6 and 18.0).

NOTE: A severe AE is NOT the same as a serious AE, which is defined in Section 10.4.

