**10.52 Death**

**Note: A death on study requires both routine and expedited reporting regardless of causality, unless as noted below. Attribution to treatment or other cause must be provided.**

Any death occurring within 30 days of the last dose, regardless of attribution to an agent/intervention under an IND/IDE requires expedited reporting within 24-hours.

Any death occurring greater than 30 days with an attribution of possible, probable, or definite to an agent/intervention under an IND/IDE requires expedited reporting within 24-hours.

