### 10.62 Submit via appropriate MCCC Case Report Forms (i.e., paper or electronic, as applicable) the following AEs experienced by a patient and not specified in Section 10.6:

10.621 Grade 2 AEs deemed *possibly, probably, or definitely* related to the study treatment or procedure.

10.622 Grade 3 and 4 AEs regardless of attribution to the study treatment or procedure.

10.623 Grade 5 AEs (Deaths)

10.6231 Any death within 30 days of the patient's last study treatment or procedure regardless of attribution to the study treatment or procedure.

10.6232 Any death more than 30 days after the patient's last study treatment or procedure that is felt to be at least possibly treatment related must also be submitted as a Grade 5 AE, with a CTCAE type and attribution assigned.

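### Note h of the test schedule and Section 10 set different rules for which adverse events and deaths are recorded in the 30 days after the last dose

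*Combined protocol and SAP*

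**What the plan says.** **Section 4.1, note h.** A nurse contacts the patient 30 days after the last dose, "or at the time of initiation of subsequent treatment if started before 30 days". For late events, "Grade 3 or higher adverse events at least possibly related to study treatment and deaths due to any cause should be reported" on the follow-up/event-monitoring form. This applies if they are not already on the last cycle's adverse event form and if "they occurred prior to any subsequent treatment and 30 days post-end of treatment". I read the last clause as meaning within 30 days of the end of treatment.

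**Section 10.**
- 10.41 covers the 30 days after the last administration and requires every serious adverse event (SAE), related or not. Its footnote 1 adds related SAEs after day 30.
- 10.52: "Any death occurring within 30 days of the last dose, regardless of attribution to an agent/intervention under an IND/IDE requires expedited reporting within 24-hours".
- 10.622 asks for "Grade 3 and 4 AEs regardless of attribution to the study treatment or procedure". 10.621 asks for Grade 2 events judged at least possibly "related to the study treatment or procedure".
- 10.6231 makes a Grade 5 event of "Any death within 30 days of the patient's last study treatment or procedure regardless of attribution to the study treatment or procedure". 10.6232 adds later deaths that are possibly related.
- 10.1 item f: "All AEs reported via expedited mechanisms must also be reported via the routine data reporting mechanisms".
- 10.7 sends late events after active monitoring to a Forms Packet, which is not among the documents.

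**Other sections.** 4.2 continues event monitoring, with death as a reporting point, after subsequent therapy and up to three years from registration. 16.42 tabulates the maximum grade per event type per patient, takes attribution into account as an addition, and states no collection window. 16.52 promises a review of Grade 4 and 5 events judged unrelated or unlikely to be related.

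**The concern.** Note h is the instruction that staff have in hand at the 30-day contact, and it names the form to fill in. It differs from Section 10 in two ways: it filters non-fatal events by attribution, and it closes at the start of new therapy, for deaths as well. Nothing in the protocol says which rule prevails.

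At stake is the safety objective (2.24). With two collection rules and no window in 16.42, the safety tables could differ according to which rule a coordinator followed. An unrelated Grade 4 event that is never collected also cannot have its attribution checked, which is what 16.52 sets out to do.

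**Working it through.** The documents state no figure on this point, so the check is a comparison of the rules for one period, the 30 days after the last dose.

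| Event | Note h | Section 10 | Result |
|---|---|---|---|
| Death, any cause, before new therapy | Kept | Required (10.52, 10.6231) | Agree |
| Death after new therapy starts | Not kept | Required (10.52, 10.6231) | Conflict |
| Unrelated non-fatal SAE | Not kept | Required (10.41), also in routine data (10.1 item f) | Conflict |
| Related Grade 3+ non-fatal SAE after new therapy starts | Not kept | Required (10.41), also in routine data (10.1 item f) | Conflict |
| Non-serious related Grade 3-4, before new therapy | Kept | Taken by 10.622 | Agree |
| Non-serious unrelated Grade 3-4 | Not kept | 10.622 takes any attribution but states no post-treatment window | Arguable |
| Non-serious related Grade 3-4, after new therapy starts | Not kept | 10.622, no window stated | Arguable |
| Non-serious related Grade 2 | Not kept | 10.621, no window stated | Arguable |

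**Two constructed patients.**
1. Last dose on day 0, new therapy on day 10, death on day 25. Since 25 < 30, this is a Grade 5 event under 10.6231 and an expedited report under 10.52. Since 25 > 10, note h does not take it as a late event. The contact was moved to day 10, so note h schedules no later adverse event contact in the window.
2. Unrelated Grade 4 pneumonia on day 15 with admission of at least 24 hours, no new therapy. It is serious by 10.41's hospitalization criterion, so it is reportable and enters the routine data. Note h does not ask for it.

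**Effect on 16.42.** During treatment, 10.622 brings in Grade 3-4 events of any attribution. If note h is applied after treatment, only possibly related ones come in. One table would then mix two rules, because 16.42 sets no window.

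**Effect on the stopping rule (16.52).** The rule is 5 or more of the first 15 patients with an at least possibly related Grade 4+ non-hematologic event. Note h keeps such events within 30 days and before new therapy, so only those after new therapy could be missed. As an illustration with assumed values, take a true rate of 30% and a captured fraction c, so q = 0.30c and

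P(trigger) = 1 − Σ(k=0..4) C(15,k) q^k (1−q)^(15−k)

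- c = 1.0: q = 0.30, P = 0.485
- c = 0.9: q = 0.27, P = 0.381
- c = 0.8: q = 0.24, P = 0.281

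The rule would respond to missed events, but the documents give no value for c. Because note h keeps most qualifying events, c should lie close to 1.

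**The case against.** The strongest reply is that note h governs only what goes on one form as a late event and does not switch off Section 10. The duties in 10.41, 10.52 and 10.62 stand with no exception for new therapy, 10.1 item f carries expedited events into the routine data, and 4.2 records deaths after subsequent therapy. Both constructed patients are therefore reportable. This stands. A reader might infer that the plan discards deaths after new therapy, or that note h keeps related events only. The documents support neither: Section 10 still requires those deaths, and note h itself keeps deaths from any cause before new therapy.

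Second, 10.622 states no post-treatment window, and 10.7 refers late events to a Forms Packet that may settle the matter. This also stands, so the conflict over non-serious Grade 3-4 events is arguable while the conflict over deaths and SAEs is firm.

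Third, stopping collection at new therapy keeps the next regimen's toxicity out of the tables. That is a legitimate aim, but recording the start date of that therapy achieves it without contradicting 10.52 and 10.6231.

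The reply does not remove the practical risk. Being reportable elsewhere does not help if the person making the contact works from note h, and 4.2 records a death without saying that it becomes a Grade 5 adverse event.

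**Conclusion.** The point holds as a conflict between two stated collection rules for the same 30 days. It is firm for deaths after new therapy and for SAEs that note h omits, and arguable for non-serious Grade 3-4 and related Grade 2 events. Non-serious unrelated Grade 3-4 events are the main group with no other clear route into the data.

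The consequence is a risk that depends on staff following note h. A reader might go further and conclude that safety is understated in patients who stop early. The documents do not show this: they do not say how many patients start new therapy within 30 days, and toxicity that leads to stopping begins on treatment and belongs on the last cycle's form. The 20-day half-life in 15.14 gives 0.5^(30/20) = 0.354 of daratumumab remaining at day 30 by linear clearance alone. That supports keeping the window open, but it ignores the nonlinear clearance described in the same section and counts no missed events.

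The size of any loss cannot be derived. The stopping rule is probably little affected, and the primary endpoint is not touched. The conclusion assumes that note h's closing clause means within 30 days and that the Forms Packet does not already reconcile the rules.

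**What to change.** - Reword note h to agree with 10.41, 10.52 and 10.62: through 30 days after the last dose, record all deaths, all SAEs and all Grade 3-4 events of any attribution, whether or not new therapy has started. If the contact is brought forward, the remaining days still need to be covered.
- Keep the existing rules for related deaths and SAEs after day 30 (10.6232 and 10.41 footnote 1).
- Say whether related Grade 2 events (10.621) are collected after the last dose, and bring the Forms Packet instruction under 10.7 into line.
- State that single window and attribution rule in 16.42.
- Record the start date of subsequent therapy and tabulate events before and after it separately.
- Correct the footnote letter on the adverse event row of the test schedule: it is marked f, which covers immunoglobulins, while the adverse event text is in h.

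The nurse contact already exists, so the cost is mainly rewording the note and the form instruction. The downside is a few more events, some due to the next regimen, which the recorded date identifies.
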